Scientific background: When exercise training is adequately supervised and adherence is high, it has a therapeutic effect in individuals with prediabetes or type 2 diabetes mellitus (T2DM) (Little et al., 2011; Johansen et al., 2017). Many of the cardiometabolic risk factors associated with T2DM can be improved or ameliorated with weight control and diet, as well as with regular exercise. Indeed, the beneficial effects of high-intensity interval (HIIT) and resistance (RT) training on insulin resistance have been extensively studied at the level of skeletal muscle and adipose tissue (Zanuso et al., 2017). Notwithstanding the irrefutable clinical benefits of exercise in general, there is known to be individual variability in the response to different exercise interventions (Bouchard et al., 2012b), including CT (Stephens et al., 2015). Whereas some individuals, the so-called ‘responders’ improve their metabolic profile after a training intervention (*e.g.*, a decrease in fasting glucose) others, the ‘non-responders’ show no response or even an opposite response (Boulé et al., 2005). From a statistical viewpoint, a non-response for a given variable is a lack of difference between a control and a treatment condition. The non-responder phenomenon has been shown in a non-negligible proportion of participants in exercise intervention studies, for instance, in 4–9% of adults at risk for T2DM (Phillips et al., 2017) or in 21% of patients with T2DM (Stephens et al., 2015). **Objectives:** To investigate the effects of a 20-week CT intervention on cardiovascular risk factors such as body composition, blood pressure and lipid profile among adult women with hyperglycaemia. A secondary aim was to report prevalence of non-responders for the different study outcomes. **Design:** An experimental, and randomized control clinical study. **Methods:** Physically inactive overweight/obese and hyperglycaemic adult women between 20 and 50 years, will be randomly assigned to a 20-weeks of an exercise intervention group or to a control (non-exercise) group. Comorbidities indices for body composition [body mass, waist circumference (WC), fat and lean mass], blood pressure and metabolic profile (total, LDL- and HDL-cholesterol, triglycerides, and fasting glucose) will be assessed before and after the 20-week intervention. The clinical trials will be taken in the Family Healthcare Center *Tomás Rojas* of the city of Los Lagos, Chile, which is a public healthcare centre of this country. We hope to apply the following eligibility criteria a) age between 30 and 59 years, b) not living in a rural area, c) physical activity levels [as assessed by the International Physical Activity Questionnaire (IPAQ) < 600 metabolic equivalents (MET)·min/week, d) non-involvement in regular exercise during the previous 6 months, e) fasting glucose of 100–125 mg/dL, and f) 1+ values above (or below for HDL-cholesterol) normal cutoffs for: body composition [*i.e.*, WC >


Statistical Analysis Plan (SAP): We will apply 2 main forms of statistical analyses a) to report the pre-post changes in mean terms, and b) to report the results according with the inter-individual responses based on the technical error criteria, where according with the error calculated in the three previous measurements registered by the sample that was voluntary. Thus, for example, we will classify the subjects in responders and non-responders by the technical error of measurement, and additionally, we will classify the subjects according with a responder and non-responder clinical criteria, where we will classify as responders to all subjects who can be able of changing an initial adverse clinical altered profile for a healthy new classification. Thus, the specific statistical methods that we hope to apply for each analysis are; test of normality and homoscedasticity assumptions using Shapiro-Wilk and Levene's tests, the Student's *t* test for the identification of differences at baseline. An ANCOVA will be conducted (for potential confounders outcomes) in those altered baseline differences outcomes. We also hope to apply the repeated measures of two-way (group, time) to assess occurrence of an actual training effect [*i.e.*, $p < 0.05$ for the interaction (group \times time) for the different study outcomes]. Among the specific statistical methods we hope to apply the Bonferroni *post hoc* test we hope to apply when we can be seen test differences among groups. Similarly, we hope to apply the Cohen's *d* test in order to detect effect size, using the threshold values of 0.20, 0.60, 1.2, and 2.0 for small, moderate, large, and very large effects, respectively (Hopkins et al., 2009), with 95% confidence intervals (CI). The alpha level was fixed at $P < 0.05$ for statistical significance.

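### The responder analysis labels women from one pre-post change and never estimates whether true response varies, so non-responders could be reported even if training helped every woman equally

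*Combined protocol and SAP*

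**What the plan says.** The Scientific background treats differing response as settled: "there is known to be individual variability in the response to different exercise interventions". The Objectives add: "A secondary aim was to report prevalence of non-responders for the different study outcomes". The Methods provide for assessment before and after the 20 weeks in a randomised exercise group and a non-exercise control group, so each woman contributes one change per outcome.

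The SAP names two main forms of analysis. The first reports mean pre-post change; the second is "to report the results according with the inter-individual responses based on the technical error criteria". For the second it gives two rules:

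- **Technical error rule:** "we will classify the subjects in responders and non-responders by the technical error of measurement". The error is obtained "according with the error calculated in the three previous measurements registered by the sample that was voluntary". Its size, the interval between those measurements and the multiple used as the cut are not given.
- **Clinical rule:** a responder is a woman capable of "changing an initial adverse clinical altered profile for a healthy new classification".

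The remaining methods (t test, ANCOVA, two-way repeated measures, Bonferroni, Cohen's d) concern means. Spread enters only as an assumption check: "test of normality and homoscedasticity assumptions using Shapiro-Wilk and Levene's tests".

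The Scientific background also offers a definition: "From a statistical viewpoint, a non-response for a given variable is a lack of difference between a control and a treatment condition". That is a contrast between conditions, which labelling a woman on her own pre-post change does not use.

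**The concern.** An observed change mixes three things: the effect of training on that woman, measurement error, and whatever would have happened over 20 weeks without training. With one change per woman these cannot be separated individually. A non-responder label may mean that training did nothing for her, or that it helped as much as it helped anyone and her two readings happened to fall unfavourably.

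Whether women differ in true response is a question about spread. The control arm shows how much change varies without training, and extra spread in the exercise arm is the sign of differing response, under an assumption given below. The plan has the data for this comparison but does not make it. Moving the cut, or comparing responder counts between arms, would not supply it.

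At stake is the reading of the secondary aim. A reported percentage of non-responders would naturally be taken as the proportion of women for whom training does not work, when the data might be compatible with one common effect. The analysis of mean effects is not touched.

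**Working it through.** The plan states no figure for this analysis (no sample size, TE, cut, SD or expected effect), so there is nothing to reproduce. The check asks what the rules would report if there were no variation in true response.

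**Technical error rule.** Work in units of TE. Every woman has the same true gain d. The observed change is Normal with mean d and SD s, and a woman is a non-responder if her change is below the cut k:

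share = Φ((k − d) / s)

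All three inputs are assumed. If TE captures all within-woman variation, s = √2 = 1.41, because a change is the difference of two readings. If 20-week fluctuation adds as much variance again to each reading, s = √(2 × 2) = 2.

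| Cut k | Common gain d | SD of change s | (k − d)/s | Labelled non-responders |
|---|---|---|---|---|
| 2 | 3 | 2 | −0.50 | 31% |
| 2 | 3 | 1.41 | −0.71 | 24% |
| 2 | 4 | 2 | −1.00 | 16% |
| 2 | 5 | 2 | −1.50 | 7% |
| 1 | 4 | 1.41 | −2.12 | 2% |
| 1 | 5 | 1.41 | −2.83 | 0.2% |
| 2.83 | 2 | 1.41 | 0.59 | 72% |

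True variation in response is zero in every row. In the last row the common gain lies below the cut.

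With the first row's settings and no training effect, Φ((0 − 2)/2) = 16% of controls would be labelled responders.

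**Clinical rule.** Take fasting glucose, with the eligibility range of 100–125 mg/dL from the Methods. Assume baselines uniform over that range, healthy meaning below 100, and the same fall D in every woman. Those who start at 100 + D or above stay in the adverse class:

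share = (25 − D) / 25

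For D = 5, 10 and 15 mg/dL this gives 80%, 60% and 40%. Noise of SD 5 mg/dL hardly alters it (78%, 60%, 40%). The label reflects starting distance from the threshold.

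**What the arms can show.** In 20,000 simulated trials at each of 15, 30 and 60 women per arm (k = 2, d = 3, s = 2 in both arms), the mean difference in variance of change, exercise minus control, was 0.004, 0.000 and −0.002 TE². That correctly indicates no differing response. The TE rule labelled 31% of the exercise arm non-responders in the same trials.

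**Precision of that estimate.** Assume 30 women per arm, with individual response independent of untrained change.

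- SD of individual response equal to the control SD of change: variance ratio 1 + 1² = 2. An F test at one-sided 2.5%, which corresponds to a two-sided 95% CI lying above zero, has power 45%; a simulated percentile bootstrap interval gives about 46–47%.
- SD of individual response half the control SD of change: variance ratio 1 + 0.5² = 1.25. The F test gives 8% and the bootstrap about 10%.

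**The case against.** The strongest defence is that the aim is descriptive. The plan promises a prevalence, not a test of whether response varies, and takes variability from earlier work. The TE rule is also a deliberate allowance for measurement noise. Both points are fair. But allowing for error in placing a cut does not estimate variation in response, and a TE from earlier repeat readings in a volunteer sample need not cover 20 weeks of ordinary fluctuation. Nor is the label neutral: it says that the woman did not respond.

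Levene's test could reveal unequal spread if run on change scores by arm. The SAP lists it only as an assumption check and does not connect it to the secondary aim.

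A second objection concerns the remedy. The difference in variances measures response variability only if individual response is uncorrelated with the change a woman would have had untrained; with a negative correlation, equal spreads can hide differing response. Uneven attendance can widen the exercise arm. The estimate is also imprecise, so a strict rule allowing mention of differing response only when the interval lies above zero would often turn low power into an answer. These points stand. They argue for reporting the estimate with its assumptions and reading the prevalence beside it, without such a rule.

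Three stronger readings are tempting and not supported:

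- That the trial will report a large spurious share. The size depends on inputs the documents do not give, and can be below 1%.
- That the shares of 4–9% and 21% cited in the background are artefacts. A common effect could produce such figures, but that is a property of the normal curve and says nothing about those studies.
- That women do not differ in response. The documents contain no evidence either way.

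**Conclusion.** The point holds as a gap in the secondary analysis. Nothing planned estimates between-woman variation in true response, and the labels can yield non-responders under one common effect. The size is conditional: 31% with a common gain of 3 TE, SD of change 2 TE and cut 2 TE, and from under 1% to about 70% across the inputs tried, all of them assumed. The clinical rule gives 40–80% in the glucose example, on an assumed uniform baseline.

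The change should be made, but it concerns a secondary, descriptive aim and leaves the group-by-time analysis intact. A reader might infer that the randomised comparison of spreads settles the question. It does not: it rests on the no-correlation assumption and, at plausible arm sizes, will often be inconclusive.

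**What to change.** Add to the SAP, alongside the prevalence table and for each outcome:

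1. The SD of the 20-week change in each arm, using all randomised women with both values. The 70% compliance requirement in the Methods removes women from the exercise arm only and could distort the comparison of spreads.
2. The difference in variances of change, exercise minus control, with a 95% CI, and the signed SD of individual response (the square root of the absolute difference, keeping its sign). Show negative differences as such.
3. A statement that this assumes individual response is uncorrelated with the change a woman would have had untrained, and that uneven attendance, including that of women below 70% compliance, can add to the exercise-arm spread.
4. A rule of interpretation: where the CI includes zero, say that the data do not show differing response, add that this is not evidence of equal response, and do not present the labelled share as the proportion of true non-responders.

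The cost is SAP wording and a few lines of code on data already collected. The downside is imprecision: at the assumed 30 per arm, several outcomes are likely to be inconclusive. The estimate also does not repair the clinical rule, so a note is needed that those labels depend partly on baseline distance from the threshold.

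### The technical-error responder rule judges a 20-week change with an error from three earlier repeat measurements and makes no use of the control arm's change over the same 20 weeks

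*Combined protocol and SAP*

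**What the plan says.** The protocol's Objectives include individual response: "A secondary aim was to report prevalence of non-responders for the different study outcomes". The Statistical Analysis Plan gives two rules for it.

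- **Technical-error rule.** The SAP states that "we will classify the subjects in responders and non-responders by the technical error of measurement", with the error obtained "according with the error calculated in the three previous measurements registered by the sample that was voluntary". It does not give the spacing of the three measurements, the number of volunteers, whether they are trial participants, the TE formula, or the multiple of TE that separates the two labels.
- **Clinical rule.** A woman is a responder if she succeeds in "changing an initial adverse clinical altered profile for a healthy new classification". This rule does not use the TE.

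Under Methods, women are randomised to exercise "or to a control (non-exercise) group", and the body-composition, blood-pressure and metabolic outcomes "will be assessed before and after the 20-week intervention". The Scientific background states that, statistically, "a non-response for a given variable is a lack of difference between a control and a treatment condition". At the level of means, the SAP uses the group-by-time interaction "to assess occurrence of an actual training effect".

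**The concern.** An error estimated from repeat measurements contains only the variation that was present between those repeats. A change over 20 weeks in weight, waist, glucose, lipids or blood pressure also contains slower biological fluctuation, season and diet, and any trend common to everyone in the study. If the three repeats were taken close together, a cut scaled to their error treats part of that ordinary variation as individual response or individual failure to respond.

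The trial will observe the relevant variation directly, because the controls are followed over the same 20 weeks. The TE rule does not use them. It therefore departs from the background section's description of non-response as a comparison with control.

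At stake are the label given to each woman under the TE rule and the non-responder prevalence counted from those labels.

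**Working it through.** The documents give no TE value, multiple, SD or sample size, so there is no planned figure to reproduce. What can be checked is how the rule behaves over a range of assumptions.

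**Inputs**

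- Interval: 20 weeks, with one assessment before and one after (Methods).
- Cut: m × TE. The SAP does not state m; 1, 2 and 2.77 are assumed.
- r: the within-person SD over 20 weeks divided by the TE. Not in the documents; 1 to 3 is assumed.
- d: mean favourable change shared by both arms, in TE units. Not in the documents; 0 to 1 is assumed.

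**False response with no true change.** With independent errors at the two assessments, the change has SD √2 × r × TE, so

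P(false response) = Φ(−m / (√2 r)).

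For m = 2 and r = 1.5 this is Φ(−2 / 2.121) = Φ(−0.943) = 17.3%.

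| Cut | r = 1 | r = 1.5 | r = 2 | r = 3 |
|---|---|---|---|---|
| 1 TE | 24.0% | 31.9% | 36.2% | 40.7% |
| 2 TE | 7.9% | 17.3% | 24.0% | 31.9% |
| 2.77 TE | 2.5% | 9.6% | 16.4% | 25.7% |

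To hold false response at 5% one-sided, the cut must be 1.645 × √2 × r = 2.33 r in TE units: 2.33, 3.49, 4.65 and 6.98 for r = 1, 1.5, 2 and 3.

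**Shared drift.** P = Φ((d − m) / (√2 r)). At 2 TE, a drift of 1 TE raises false response from 7.9% to 24.0% at r = 1, and from 24.0% to 36.2% at r = 2. At 1 TE, a drift of 1 TE gives 50% whatever r is. Drift therefore matters even when the TE has the right spread.

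**False non-response.** For a woman whose true change lies 1 TE beyond the cut, P(labelled non-responder) = Φ(−1 / (√2 r)): 24.0% at r = 1 and 36.2% at r = 2.

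**Net effect on prevalence.** Two illustrations at a 2 TE cut without drift:

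- Nobody truly responds. Counted non-response is 100 − 7.9 = 92.1% at r = 1 and 100 − 24.0 = 76.0% at r = 2. It falls as r rises.
- 21% are true non-responders with no change (one of the prevalences cited in the background, used here only as an illustration) and the rest truly change by 3 TE. Counted non-response is 0.21 × 0.921 + 0.79 × 0.240 = 38% at r = 1, and 0.21 × 0.760 + 0.79 × 0.362 = 45% at r = 2. It rises as r rises.

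The sign of the error in prevalence therefore depends on the true effects.

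**Precision of the TE.** With three measurements per volunteer there are 2 degrees of freedom each. The 95% limits are 0.77 to 1.44 times the estimate with 10 volunteers and 0.87 to 1.18 times with 40 (numbers assumed).

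**The case against.** The strongest reply is that the documents do not show the cut to be too small. The spacing of the three measurements is not given; if they were well separated, the TE already holds some biological variation and r may be near 1. Nor is the multiple given, and a generous one can offset a modest r: at 2.77 TE with r = 1.5 false response is 9.6%, close to the 7.9% at 2 TE with r = 1. This stands. A reader might infer that the threshold is demonstrably too small, or that the repeats were certainly taken before the trial in other people. The first depends on unstated facts; the second is only one reading of the SAP's wording.

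A reader might also infer that non-response will be understated. That follows only for women with no true change. Extra variation also pushes true responders below the cut, and the second illustration shows counted non-response rising.

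A third tempting reading is that the whole secondary aim rests on this threshold. It does not: the clinical-category rule is separate and does not use the TE.

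Finally, replacing the TE with SD / √2 of the control change is not enough alone. It corrects spread but leaves shared drift in each woman's change, leaves the multiple open, and exchanges some false response for false non-response. All three points stand and shape the remedy. What the reply does not remove is that nothing in the SAP shows the TE suits a 20-week change, and that the control data which could show it are left out of the rule.

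**Conclusion.** The mismatch is real and worth correcting. An error from three earlier repeats in a volunteer sample is applied to a 20-week change, with no adjustment from the controls, and this sits poorly with the protocol's own description of non-response. If the repeats were closer together than 20 weeks, or if there is shared drift, the TE-based labels and the TE-based prevalence are unreliable, in a direction that cannot be stated in advance.

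For a woman with no true change, false response is 8%, 17% or 24% at 2 TE, and 24%, 32% or 36% at 1 TE, for a 20-week error of 1, 1.5 or 2 times the TE. These figures rest on assumed multiples and ratios, normal and independent errors, and no drift. For scale, the background cites non-response of 4–9% and 21% in other exercise studies, so labelling error could be of the same order as the quantity to be reported.

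The damage is confined to the TE-based part of the secondary aim. The group-by-time test and the clinical-category rule do not depend on it.

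**What to change.** In the SAP, for each marker:

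1. Subtract the control arm's mean 20-week change from each woman's change.
2. Set the responder cut as a stated multiple of the control-arm typical error, SD of control change / √2. Fix the multiple before the data are seen.
3. Report the proportion of responders in both arms under the same rule.
4. Keep the SAP's own TE cut as a sensitivity analysis, stating its formula, multiple, volunteer sample and spacing, and report it in both arms too. The control proportion under that cut shows directly how often it labels unexercised women as responders.

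The cost is SAP wording only; the data are already planned. If the TE already reflects 20-week variation, the two cuts will be similar and little is lost.

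There are three downsides to disclose.

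- The control SD is itself uncertain: 21 controls (an assumed number) give 20 degrees of freedom and 95% limits of about 0.77 to 1.44 times the estimate.
- With roughly normal changes, the control proportion under the new cut is largely set by the multiple (about 24% at 1 and 8% at 2), so it serves as a benchmark for the exercise arm and not as a finding.
- A wider cut lowers false response at the price of false non-response. With r = 2 and a true change of 3 TE, moving the cut from 2 to 4 TE lowers false response from 24% to 8% but raises false non-response from Φ(−1 / 2.828) = 36% to Φ(1 / 2.828) = 64%. The counted proportion should therefore be presented as the result of a stated rule, beside the control proportion, and not as the true prevalence of non-response.

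### Responder status is never compared between arms, so the planned non-responder prevalence cannot be read as response or non-response to exercise

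*Combined protocol and SAP*

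**What the plan says.** The protocol's Objectives state: "A secondary aim was to report prevalence of non-responders for the different study outcomes". Its Scientific background says that, statistically, "a non-response for a given variable is a lack of difference between a control and a treatment condition". Under Methods, women are randomized to exercise or to a non-exercise control, and outcomes "will be assessed before and after the 20-week intervention".

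The SAP describes two analyses, one of mean changes and one of inter-individual responses. For the second it gives two rules:

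- **Technical error:** "we will classify the subjects in responders and non-responders by the technical error of measurement". The error comes from "the error calculated in the three previous measurements registered by the sample that was voluntary". The multiple of the error, the direction of change and the spacing of those measurements are not stated.
- **Clinical:** the plan will "classify as responders to all subjects who can be able of changing an initial adverse clinical altered profile for a healthy new classification".

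The methods then listed are Shapiro-Wilk and Levene's tests, a baseline t test, ANCOVA, two-way (group, time) repeated measures, Bonferroni post hoc tests and Cohen's d with 95% CI. The group-by-time interaction is the one given the task "to assess occurrence of an actual training effect".

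**The concern.** Both rules compare a woman with her own earlier value. A woman who crosses a cutoff may have responded to exercise, or she may have crossed it through measurement error or ordinary variation over 20 weeks. If the value that qualified her for the trial also serves as her baseline, regression to the mean adds to this. A single-arm count cannot separate these causes. The control arm can show how many responders appear without exercise, but the plan does not say it will be used for that.

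The protocol's background describes non-response as a control-versus-treatment matter, and the planned prevalence does not supply that contrast. At stake is the meaning of the stated secondary aim: a figure such as 20% non-responders would invite the reading that exercise fails one woman in five, which the analysis cannot support.

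**Working it through.** **Is a comparison stated?** The listed methods suit continuous outcomes. Levene's test compares variances, but only as an assumption check. No test of proportions, risk difference, odds ratio or interval is named for responder status, and no comparison of the spread of change between arms.

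**Inputs.** The plan gives no figure to reproduce: no TE value, cutoff multiple, expected responder rate or sample size. What follows are illustrations under stated assumptions, not estimates for this trial. From the documents come only the glucose entry range (100–125 mg/dL), the two rules and the two-arm design.

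**TE rule, no true change.** Let the error SD at each visit be k×TE and the cutoff m×TE. The SD of change is k√2×TE, so P(called responder) = 1 − Φ(m/(k√2)).

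| Assumption | m = 1 | m = 2 |
|---|---|---|
| k = 1, one reading per visit | 0.240 | 0.079 |
| k = 2 (20-week within-woman SD of 2×TE) | 0.362 | 0.240 |
| Mean of three independent readings per visit: 1 − Φ(m/√(2/3)) | 0.110 | 0.007 |

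**TE rule, every woman truly improves by d×TE** (k = 1). P(called non-responder) = Φ((m − d)/√2).

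| Cutoff | d = 2 | d = 3 | d = 4 |
|---|---|---|---|
| m = 1 | 0.240 | 0.079 | 0.017 |
| m = 2 | 0.500 | 0.240 | 0.079 |

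**Clinical rule for glucose, no intervention.** Assume normal distributions with mean 95, 100 or 105, between-woman SD 8, 10 or 12 and within-woman SD 3, 5 or 7 mg/dL (27 combinations), and select women with a screening value of 100–125.

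- *Screening value is also baseline.* P(second value < 100 given first 100–125) is 0.084 at the lowest (105, 12, 3), 0.210 mid-case (100, 10, 5) and 0.431 at the highest (95, 8, 7).
- *Baseline is a new measurement.* The same 8–43% would already be below 100 at baseline. Among those still at or above 100, the simulated share below 100 at week 20 is 0.048, 0.133 and 0.312 for the same three cases.

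**Denominator of the clinical rule.** Eligibility needs only "f) 1+ values above (or below for HDL-cholesterol) normal cutoffs for" the listed measures. A woman can therefore enter while normal on a given outcome. If the rule is applied per outcome, the plan does not say how she is counted.

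**What a between-arm difference would show** (k = 1, controls unchanged, all exercisers improve by d×TE). Difference = Φ(m/√2) − Φ((m − d)/√2).

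- m = 1: 0.520, 0.682, 0.743 for d = 2, 3, 4.
- m = 2: 0.421, 0.682, 0.843.
- If only 75% improve, by 3×TE, with m = 1: 0.75 × 0.682 = 0.511, nearly the same as all improving by 2×TE (0.520).

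**Precision at assumed arm sizes.** For 76% versus 24%, the 95% half-width is 1.96 × √(2 × 0.76 × 0.24/n): 0.265 at n = 20 per arm and 0.167 at n = 50.

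**The case against.** The strongest reply is that the aim only promises to report prevalence, and a descriptive figure does that. The plan reserves its effect claim for the group-by-time test, which gives a control-treatment contrast for each variable; the background sentence on non-response can be read at that level. The SAP classifies subjects without restricting the arm, so control figures may well be tabulated, and it introduces its methods list as covering both analyses. The illustrations rest on assumed inputs: false-responder rates under the TE rule run from 1% to 36%, and at 2×TE with triplicate means the problem nearly disappears. Finally, the between-arm difference would not itself be a non-responder prevalence.

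Much of this stands. The mean analysis is sound on this point, a descriptive prevalence is consistent with the aim, the inputs are assumptions, and the difference does not recover the true share of non-responders. It does not close the gap. Even if the methods list covers both analyses, none of its methods is specified for responder status. Possible tabulation of controls is not a stated comparison. The background uses the term non-responders for individuals who train without benefit, so the causal reading is the natural one unless the plan rules it out.

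**Conclusion.** The concern holds. No between-arm contrast of responder status is stated, and prevalence against own baseline cannot be read as response or non-response to exercise. This reading of the text needs no assumed figures.

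The size does. Under the error models shown, 1–36% of unchanged women are called responders by the TE rule, and 2–50% of women who truly improve by 2 to 4×TE are called non-responders. For glucose under the clinical rule, 8–43% would count as responders without intervention if screening serves as baseline, or 5–31% of those still abnormal at a separate baseline. For scale, the background cites non-responder prevalences of 4–9% and 21%; misclassification alone can yield figures that large.

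The point is limited to the secondary aim and should be fixed before anyone is classified.

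**What to change.** 1. State in advance the TE multiple, its direction and the spacing of the three measurements. Apply both rules identically in both arms. For each outcome, report the responder proportion by arm and the exercise-minus-control difference with 95% CI.
2. Do this in all randomized women with outcome data. The 70% compliance requirement under Methods applies to the exercise arm only and would undo the protection of randomization. A compliers-only version can be a labelled sensitivity analysis.
3. If the clinical rule is applied per outcome, restrict its denominator in both arms to women abnormal on that outcome at baseline, and state whether screening values serve as baseline.
4. Describe single-arm prevalence as descriptive, not as the share of women who do not respond to exercise.
5. Optionally, compare the SD of change between arms and report the SD of individual response with 95% CI.

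The cost is SAP text and a simple analysis of pre-post data already planned in both arms; outcome data must be kept from exercise women below 70% compliance. The figures will be less striking, individual labels stay error-prone, and intervals will be wide (about ±26 points at an assumed 20 per arm, ±17 at 50). The difference must not be presented as the true non-responder share. The optional SD is weak in small arms: if it equals the control SD of change, its 95% CI in control-SD units runs from −0.65 to 1.56 at 20 per arm and from 0.34 to 1.37 at 50.
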